- Use of placebo
- Biopsy conducted solely for research purposes
- Sham surgical procedure
- None of the above

8.9 * PROCEDURES / METHODS: (REQUIRED)

For clinical research, list all study procedures, tests and treatments required for this study, including when and how often they will be performed. If there are no clinical procedures, describe the research activities.

If some of the activities would occur even if the person were not in the study, as in the case of treatment or tests performed for diagnostic purposes, **clearly differentiate between those activities that will be done solely for research purposes and those that are happening as part of routine care.**

Examples may include:

- additional scans outside standard clinical diagnosis or monitoring
- additional biopsies to collect tissue for research
- extra clinic visits
- extra lab tests not required for clinical care

If you have a procedure table, attach it to the submission with your other study documents.

Study Procedures: Potential participants will be asked brief eligibility screening questions in person or over the phone after providing verbal consent. Potential participants will provide informed consent and be screened for eligibility during the pre-enrollment screening visit. The schedule for the study procedures is shown in **Table 3**.

Participants will be compensated for their time at each visit and in responding to daily ecological momentary messages (up to a total of \$421). Participants will receive \$50 for the 2 in-office screening visits (\$20 at Screen 1 and \$30 at Screen 2), \$15 each for in-office run-in visits 1 and 2, \$40 for in-office enrollment, \$15 for remote weekly visits (1-3, 5-7, and 9-11), \$15 for in-office weekly visits (4, 8, 12), \$40 for in-office week 4 (month 1) and week 8 (month 2) visits, and \$50 for week 12 (month 3). In addition, they will receive \$0.40 for each day that they complete the daily EMA series throughout the 12-week treatment period (up to \$36). Participants will be paid by cash, visa gift cards, or by paypal.

Participants could receive a gift card (\$10) for partial screening visits. For any snowball referral that has completed a screening visit, the participant who referred the new participant will receive

\$10. If the new participant enrolls in the study, the participant who referred the new participant will receive \$40.

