PrEP ART adherence by drug levels (HIV-), viral load (HIV+)		X		X		X
Study drug MEMS adherence monitoring		X	X	X	X	

*Confirmatory tests will be performed for reactive tests. S=Screening, E=Enrollment visit /Baseline, W=weekly, M = Month (M 3 = Final visit),

8.10 STANDARD CLINICAL PRACTICE: To what extent, if any, do the planned research procedures differ from the care that people would otherwise receive at this institution or the study site if not being done locally:

All participants will receive substance use counseling and psychotherapy for reducing methamphetamine use disorder. There is no FDA approval to use oral Naltrexone for reducing meth use disorder. This differs from the care that people would otherwise receive at the institution.

8.11 INSTRUMENTS: List all questionnaires, surveys, interview, or focus group guides that will be used for this study:

Table #4 provides a summary of the study measures:

TABLE 4: SUMMARY OF MEASURES

Data Source

Schedule

PRIMARY PREDICTOR VARIABLE

Trial arm (ION+EMI, placebo+EMI)

Randomization

En

OUTCOME VARIABLES

Primary biologic outcome

Urine samples: negative vs. positive for meth

Urine samples

En, Wkly

PrEP* and ART adherence

Lab specimens

En, M 1-3,

Behavioral outcomes^{201,202}

Total # of sexual partners, by partner HIV status; number of partners using Pre-Exposure Prophylaxis (PrEP); # of partners with undetectable viral load

ACASI

En, M 1-3,

Total # of condomless sex acts on/off PrEP/ART, by partner HIV status, PrEP status and viral load status

ACASI

En, M 1-3,

Reported days/episodes meth use¹¹⁶ timeline follow-back

ACASI; EMA

En, W, M 1-3,

Other substance use (opioids, alcohol, cocaine, marijuana, ecstasy, gamma-hydroxybutyrate, etc.)

ACASI;

En, M 1-3

Injecting behaviors: needle-sharing, sharing works

ACASI

En, M 1-3

Substance use treatment (outside study)	ACASI	En, M 1-3
Barratt's Impulsivity Scale ¹⁸⁶	ACASI	En, M 1-3
Substance use antecedences: Brief Substance Use Craving ¹⁷² ; Visual Analog Scale Craving Scores ¹⁷³ ; Daily Craving ¹⁷⁴ ; Affect, Mood ¹⁷⁵ ; Sexual Excitation Scale/Sexual Inhibition short form ¹⁸⁷ , Perceived Stress Scale ¹⁷⁶ , EMA Risk Antecedents ¹⁹⁷	ACASI; EMA	En, W, M 1-3, Daily

Additional covariates

Demographics (age, race, education, income)	ACASI	En
Brief Symptom Inventory ²⁰⁴ , Severity of Dependence ²⁰⁵	ACASI	En, M 1-3,

Study Drug, MEMs and EMA adherence

Timing of pill via MEMs cap openings	MEMS Caps	Daily

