Specific Aim 1: *To determine the efficacy of ION vs. placebo in reducing meth use, as determined by the proportion of meth-positive urine tests.* As in our prior trial, a GEE Poisson model with robust standard errors will be used to compare weekly urine test results by treatment assignment; this provides easier-to-interpret risk-ratios²¹⁸ rather than odds-ratios. The treatment effect of ION vs. placebo will be modeled as linearly increasing and summarized by the between-group difference in means at 12 weeks, net of any baseline difference. *Minimum Detectable Effects (MDEs) with sample size:* Based on the prior trial (93% retention with an 8-week follow-up), we estimate that 80% of participants will be retained at 12 weeks, and within-subject correlation will be 0.45. Under these assumptions, the study sample will have 80% power in 2-sided tests with a type-I error rate of 5% to detect net between-group differences in the reduction in sweat patch positivity of ~14.5 percentage points. In the Project iN study, we have observed reductions on meth use between 18%-22% among the ION arm, compared to placebo, in ITT and sub-group analyses.¹⁰⁹ Therefore, we believe that the reductions in meth use we are powered to detect in this aim are reasonable to anticipate. *In sensitivity analyses*, we will also evaluate between-group differences on changes in: 1) any meth-positive samples or self-report of meth use in timeline follow back; and 2) meth positivity from self-report only. Concordance of the urine testing, and self-reported measures will be examined using weighted Kappa and correlations. We recognize that meth use is a stigmatized behavior that may be underreported. Hence, in the event of discrepancies between urine results and timeline follow back data on meth use, we will treat the urine test results as the gold standard. *Additionally, we will analyze participant's perception of whether the EMI prompts had effects on various HBM constructs and explore whether these moderate treatment effects on meth use.*^{119,120}

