For the safety to participants and staff during COVID-19, the study has been designed with hybrid visits according to Interim UCSF research guidelines. The weekly visits (weeks 1, 2, 3, 5, 6, 7, 9, 10 and 11) will be conducted remotely through zoom. The participant will be given single M-AMP urine test kits and urine collection bottles at the in-office visits and trained how to conduct the urine test. The participant is asked to provide a urine sample in the urine collection bottle before the video visit. The participant will dip the M-AMP stick in the urine during the video visit and the dip stick will be shown to the counselor. Due to video resolution, a faint red line may not be able to be viewed by video. If this happens, the participant will be asked to take a picture of the dip stick and upload it to a secure portal or an encrypted e-mail. After IRB approval, we will test this option on RedCAP through the participant survey invitation and embedded image upload option.

13.5 * BENEFITS: (REQUIRED) Note: These are the benefits that the IRB will consider during their review. They are not necessarily appropriate to include in the consent form.

Possible immediate and/or direct benefits to participants and society at large (check all that apply):

Positive health outcome (e.g. improvement of condition, relief of pain, increased mobility, etc.)

Closer follow-up than standard care may lead to improved outcomes or patient engagement

Health and lifestyle changes may occur as a result of participation

Knowledge may be gained about their health and health conditions

Feeling of contribution to knowledge in the health or social sciences field

The research presents a reasonable opportunity to further the understanding, prevention, or alleviation of a serious problem affecting the health or welfare of children

Other benefit (describe below)

None

Briefly discuss the other possible benefits:

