For the safety to participants and staff during COVID-19, the study has been designed with hybrid visits according to Interim UCSF research guidelines. The weekly visits (weeks 1, 2, 3, 5, 6, 7, 9, 10 and 11) will be conducted remotely through zoom. The participant will be given single M-AMP urine test kits and urine collection bottles at the in-office visits and trained how to conduct the urine test. The participant is asked to provide a urine sample in the urine collection bottle before the video visit. The participant will dip the M-AMP stick in the urine during the video visit and the dip stick will be shown to the counselor. Due to video resolution, a faint red line may not be able to be viewed by video. If this happens, the participant will be asked to take a picture of the dip stick and upload it to a secure portal or an encrypted e-mail. After IRB approval, we will test this option on RedCAP through the participant survey invitation and embedded image upload option.

15.5 * REPORTABILITY: Do you anticipate that this study may collect information that State or Federal law requires to be reported to other officials, such as elder abuse, child abuse, or threat to self or others: (REQUIRED)

Yes No

The confidentiality and privacy section of the consent form should include this as a possible risk of participation.

*** Describe the types of reportable information the research team may encounter and provide the details of the reporting plan: (REQUIRED)**

Exceptions to confidentiality for participants are those required by law such as a diagnosis of sexually transmitted infections (STIs) including HIV, CD4 and Viral Load and threat of imminent action on suicidal or homicidal ideation. At any time, persons judged by project investigators to be a danger to self or others, will be escorted to San Francisco General Hospital. All staff, including research assistants and counselors, receive yearly training for identifying suicide /homicide risk and/or dangerous intoxication, and de-escalation of agitated or angry persons. All staff are trained to appropriately respond to these situations by immediately contacting a study clinician to evaluate the participant.

15.6 CERTIFICATE OF CONFIDENTIALITY: Will this study obtain a Certificate of Confidentiality:

Yes No

Please include the recommended Certificate of Confidentiality language in the consent form.

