California regulations require that positive HIV test results be reported to the county public health department, even if it is not a new diagnosis for the individual. HIV test result reporting includes CD4+ count (or T-cell count), viral load, and viral genotype for positive results. This information is used to track the disease statewide and nationwide.

The report includes details like participant name, social security number, and other identifying information. The San Francisco Department of Public health may share the results with the participant's home county health department if they do not live in San Francisco County. Other than this required reporting, test results will be treated confidentially by the study staff and personally identifying information will not be reported to other departments or agencies.

15.12 * PATIENT RECORDS: Will health information or other clinical data be accessed from UCSF Health, Benioff Children's Hospital Oakland, or Zuckerberg San Francisco General (ZSFG): (REQUIRED)

Yes No

15.15 * HIPAA - PERMISSION TO ACCESS SENSITIVE DATA: Does the research require access to any of the following types of health information from the medical record: (check all that apply) (REQUIRED)

- Drug or alcohol abuse, diagnosis or treatment
- HIV/AIDS testing information
- Genetic testing information
- Mental health diagnosis or treatment
- None of the above

Important note: Ensure that participants initial the corresponding line(s) in Section C of the HIPAA authorization form during the consent process.

15.19 * DATA COLLECTION AND STORAGE: (check all that apply): (REQUIRED)

Collection methods:

- Electronic case report form systems (eCRFs), such as OnCore or sponsor-provided clinical trial

management portal

- UCSF ITS approved Web-based online survey tools: Qualtrics or RedCap
- Other web-based online surveys or computer-assisted interview tool
- Mobile applications (mobile or tablet-based)
- Text Messaging
- Wearable devices
- Audio/video recordings
- Photographs
- Paper-based (surveys, logs, diaries, etc.)
- Other:

* Specify what other methods will you use to collect data: **(REQUIRED)**

If the counselor is unable to read the urine dip stick through the remote video visit, the participant will be asked to take a photo of the dip stick result and upload this to a secure portal or encrypted e-mail.

* What online survey or computer assisted interview tool will you use: **(REQUIRED)**

- Qualtrics (Recommended)

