**07/13/2021**

## Statistical Analyses

We will use generalized estimating equations (GEE) to estimate treatment effects on repeated study outcomes. Primary analyses will be by intention-to-treat (ITT). In prior trials, we had excellent visit retention and study completion. Nonetheless, in this high-risk population, missing data may be encountered. We will conduct sensitivity analyses imputing all missing urine samples as positive, adjusting for baseline correlates of missingness, and using inverse probability of censoring weights.

**Specific Aim 1:** *To determine the efficacy of ION vs. placebo in reducing meth use, as determined by the proportion of meth-positive urine tests.* As in our prior trial, a GEE Poisson model with robust standard errors will be used to compare weekly urine test results by treatment assignment; this provides easier-to-interpret risk ratios rather than odds ratios. The treatment effect of ION vs. placebo will be modeled as linearly increasing and summarized by the between-group difference in means at 12 weeks, net of any baseline difference.

**Minimum Detectable Effects (MDEs) with sample size:** Based on the prior trial (93% retention), we estimate that 90% of participants will be retained at 12 weeks, and within-subject correlation will be 0.45. Under these assumptions, the study sample of 54 participants will have 80% power in 2-sided tests with a type-I error rate of 5% to detect net between-group differences in the reduction in urine positivity of ~24 percentage points, equivalent to a relative rate reduction of 32%. We have observed similar reductions on meth use in ITT and subgroup analyses in prior trials. Therefore, we believe that the reductions in meth use we are powered to detect in this aim are reasonable to anticipate.

**Specific Aim 2:** *To determine the efficacy of ION vs. placebo in reducing meth-associated sexual risk behaviors.* We will use GEE Poisson models with robust standard errors to assess evidence that the intervention reduces HIV risk behaviors, including number of sex partners, and number of sex partners with whom meth is used.

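### Nine of the 12 weekly primary-endpoint urine strips are read live over video, with a photo only if a reading problem is noticed and no routine image to re-read

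*Protocol*

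**What the plan says.** The primary biologic outcome in protocol Table 4 (section 8.11) is "Urine samples: negative vs. positive for meth", collected at enrollment and weekly. Section 13.4 sets the visit mode: "The weekly visits (weeks 1, 2, 3, 5, 6, 7, 9, 10 and 11) will be conducted remotely through zoom". The payment text in section 8.9 refers to "in-office weekly visits (4, 8, 12") and to an in-office enrollment visit.

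The reading procedure appears in the same words in sections 13.4 and 15.4: "The participant will dip the M-AMP stick in the urine during the video visit and the dip stick will be shown to the counselor". Section 13.4 then allows for limited image quality: "a faint red line may not be able to be viewed by video. If this happens, the participant will be asked to take a picture", to be uploaded to a secure portal or sent by encrypted e-mail. Section 15.19 words the trigger differently: "If the counselor is unable to read the urine dip stick through the remote video visit", a photo is requested.

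Where urine and self-report disagree, section 8.13 says "we will treat the urine test results as the gold standard". In the SAP the treatment effect is "modeled as linearly increasing and summarized by the between-group difference in means at 12 weeks, net of any baseline difference".

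The documents do not give a routine photo of every remote strip, a second reader, an indeterminate category, a rule for a doubtful line, or a statement of whether a line means positive or negative. They also do not describe how the methamphetamine strip is read at in-office visits.

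**The concern.** The photo is meant to rescue reads in which the video hides a faint line. Under the section 15.19 wording it is requested when the counselor cannot read the strip. A strip whose faint line is invisible on screen can look like a readable strip with no line. The counselor may then believe the read is complete and not ask for a photo. The safeguard is therefore least dependable for the one error the protocol names.

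Three quarters of the follow-up tests are read this way. The model uses every week to estimate the week-12 difference, so reading week 12 in the office protects the estimate only in part. Urine overrides self-report, so self-report cannot correct a misread result. The planned missing-data analyses concern samples that are absent, not samples that were read wrongly. Without a stored image of each strip, the misread rate cannot be measured from the remote reads themselves.

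**Working it through.** **Inputs**

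- Remote weeks 1-3, 5-7, 9-11; in-office enrollment and weeks 4, 8, 12 (protocol 8.9, 13.4).
- Planned difference about 24 points, a 32% relative reduction, with within-subject correlation 0.45, two-sided 5%, 80% power and 54 participants (SAP). Protocol 11.3 gives the same effect with 60. Protocol 8.13 gives a different figure, for sweat patches, which is not used here.
- Allocation 2:1, so 18 placebo and 36 naltrexone.
- Implied positivity: 24/0.32 = 75% on placebo and 75 - 24 = 51% on naltrexone.

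**Share of tests.** 9/12 = 75% of follow-up tests, or 9/13 = 69% counting enrollment.

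**The plan's own figure.** Take 13 equally spaced tests (t = 0 to 12), exchangeable correlation and a linear effect on the difference scale with a free baseline. The sum of (t - 6)² is 182.

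- Variance factor for the slope scaled to week 12: (1 - 0.45) / (182/144) = 0.435.
- SE = √[0.435 × (0.75×0.25/18 + 0.51×0.49/36)] = 0.0869.
- Minimum detectable difference = (1.960 + 0.842) × 0.0869 = 24.3 points. Power at 24 points is 78.9%. This reproduces the plan's figure.

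**Weight of the remote weeks.** Each week's share of the estimated week-12 effect is t(t - 6)/182. Over the nine remote weeks:

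(-5 - 8 - 9 - 5 + 0 + 7 + 27 + 40 + 55)/182 = 102/182 = 56%.

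The in-office weeks supply the other 80/182 = 44%, mostly from week 12 (72/182).

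**Effect of missed lines.** Let x be the share of lines at remote weeks that go unseen and are scored as absent, equal in both arms. Let p be the true positive rate.

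- If a line means positive, recorded positivity is (1 - x)p.
- If a line means negative, it is p + x(1 - p).
- In both cases the arm difference at a remote week is multiplied by (1 - x).

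The week-12 estimate is then 24 × (1 - 0.560x). Power is computed with the SE held at 0.0869.

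| Assumed x | Estimated week-12 difference | Power, 54 participants |
|---|---|---|
| 0 | 24.0 | 78.9% |
| 2% | 23.7 | 77.9% |
| 5% | 23.3 | 76.5% |
| 10% | 22.7 | 74.1% |
| 20% | 21.3 | 68.9% |

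With 60 participants, power is 82.9% at x = 0, and 80.8%, 78.5% and 73.4% at x = 5%, 10% and 20%.

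**Alternative shape.** Protocol 11.3 also expects a roughly constant difference over the 12 weeks. For a simple mean of the 12 follow-up tests the estimate is 24 × (1 - 0.75x): 23.1, 22.2 and 20.4 points at x = 5%, 10% and 20%. Power for that mean (variance 0.1875 in both arms, 54 participants) goes from 77.8% to 74.7%, 71.3% and 64.0%.

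**Risk-ratio scale.** At a remote week with true rates 75% and 51% and x = 10%:

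- Line means positive: (0.9 × 51)/(0.9 × 75) = 45.9/67.5 = 0.68, unchanged.
- Line means negative: (51 + 0.1 × 49)/(75 + 0.1 × 25) = 55.9/77.5 = 0.72, closer to 1.

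**The case against.** The best defence is that section 13.4 foresees this failure. Its wording can be read as asking for a photo whenever no line is seen, which would catch faint lines. That reading is possible, but section 15.19 states a narrower trigger and nothing says which governs. The wording needs repair under either reading.

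A reader might infer that unseen lines will be scored as absent and that nothing is kept to check them. The documents do not support that as fact. They give no scoring rule, and back-up photos are uploaded and could be re-read. Section 15.19 lists recordings and photographs among collection methods, but the tick marks are lost in the text available. What can be said is that no routine image of each remote strip is specified.

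A reader might also multiply the full 24 points by (1 - x), giving 21.6 or 19.2 points at 10% or 20%. That overstates the loss in the primary estimate. Under the linear model the true difference at most remote weeks is below 24 points, and those weeks carry 56% of the signal although they are 75% of the tests.

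The other mitigations are real but partial. Double blinding makes reader-driven differences between arms unlikely, so a false treatment effect is not the expected harm. The planned self-report and concordance analyses, and the sweat patches described in section 8.9, are indirect cross-checks. None of them re-reads a strip. Because in-office reading of this test is not described, the contrast between remote and office accuracy is itself partly inferred.

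**Conclusion.** The concern holds in a limited form. Nine of 12 weekly primary-endpoint strips are read live on video, the protocol concedes that a faint line may not show, and the photo back-up depends on recognising a problem that may not be recognisable. The likely cost is a modest loss: about 0.7, 1.3 or 2.7 points of a 24-point difference, and about 2, 5 or 10 points of power, at assumed miss rates of 5%, 10% or 20%. A trial planned at 80% power has little slack for this.

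These sizes rest on assumptions. The miss rate is not in the documents. It is taken as equal in both arms, missed lines are taken as scored absent, and only lines that also escape the photo request count. The calculation is on the difference scale. On the risk-ratio scale the estimate is unchanged if a line means positive and moves toward 1 if a line means negative, and the documents do not say which applies. They do not support a claim of bias in favour of either arm.

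**What to change.** Amend sections 13.4, 15.4 and 15.19 so that:

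- the participant photographs the strip at every remote test, within the kit's reading time, and uploads it by the route already planned;
- the remote result is scored from the stored photo, and the video serves to witness the dip;
- one written line-reading rule applies to both remote and in-office strips, stating what a line means and how a doubtful line is scored;
- the live read is used only when an upload fails, and is flagged as such;
- read mode (stored photo, live video, in-office) is recorded for each test.

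Add to the SAP a sensitivity analysis of the Aim 1 result by read mode.

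The cost is nine photos per participant, some failed uploads, and wording changes in three protocol sections and the SAP. The REDCap upload option is, by the protocol's own account, still to be tested, so it should be shown to work before scoring depends on it.
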